5.7 Other Measurements, Assessments or Methods

5.7.1 Blood Sample for Molecular Profiling of CTCs

Whole blood samples will be collected at Week 1, Week 13 and at the time of PSA progression and/or at the time of radiographic progression. Seventeen milliliters (17 mL) of

- CONFIDENTIAL -

whole blood in two 8.5 mL ACD Sol A tubes are needed at each time point to ensure at least 5 mL for AR and GR analysis. Samples will be collected on Monday-Thursday and shipped overnight to for testing per vendor instructions. Remaining samples may be stored for future biomarker analysis. Methods as described by Antonarakis et al., 2014 will be used to capture CTC and quantification of messenger RNA (mRNA) of AR-FL, AR variants and GR-FL via Quantitative reverse-transcriptase–polymerase-chain-reaction (RT-PCR) assays. AR DNA was polymerase chain reaction-amplified and the product will be analyzed.

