6.1.3 Exploratory Efficacy Endpoints

Samples were collected serially at baseline, week 13, at time of PSA progression, and time of radiographic progression and analyzed at central labs for:

- 1) Androgen receptor
 - a. AR-V7
 - b. AR-FL
 - c. AR-V7/AR-FL ratio
- 2) Glucocorticoid receptor
 - a. GR-FL
- 3) AR mutations;
 - a. L702H
 - b. W741C
 - c. F876L
 - d. T877A
- 4) Circulating tumor cell detected
- 5) Inflammatory biomarkers
 - a. IL6
 - b. IL8
 - c. TNF- α (tumor necrotic factor alpha)
 - d. sTNFR1 (soluble TNF receptor-1)
- 6) Neuroendocrine biomarkers
 - a. CgA (chromogranin A)
 - b. NSE (neuron specific enolase)
 - c. Synaptophysin

Other biomarkers may be identified for analysis and SAP will be amended accordingly prior to database lock.

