7.4.3 Analysis of Exploratory Endpoints

Unless otherwise noted, all continuous biomarker values will be summarized after log base 2 transformation. Descriptive statistics (e.g., N, mean, standard deviation, minimum, median, maximum for continuous variables; or N, frequency, and percentage for categorical variables) will be provided for baseline blood and plasma samples and by each post-baseline scheduled time point for the following endpoints;

1. AR-V7 (positive/negative status, continuous log base 2 for positive status only)
2. AR-V7 status change from baseline during the study (unchanged, positive to negative, negative to positive)
3. AR-V12/v567es (positive/negative status, continuous log base 2 for positive status only)
4. AR-V7 positive or AR-V12 positive (yes/no)
5. AR-FL (continuous log base 2)
6. Ratio of (log base 2 AR-V7)/(log base 2 AR-FL) (for positive status AR-V7)

7. GR-FL (continuous log base 2)
8. L702H (yes/no, only descriptive statistics)
9. W741C (yes/no, only descriptive statistics)
10. F876L (yes/no, only descriptive statistics)
11. T877A (yes/no, only descriptive statistics)
12. CTC detected (yes/no)
13. IL6 (continuous log base 2)
14. IL8 (continuous log base 2)
15. TNF- α (tumor necrotic factor alpha) (continuous log base 2)
16. sTNF R1 (soluble TNF receptor-1) (continuous log base 2)
17. CgA (chromogranin A) (categorical split TBD, continuous log base 2)
18. NSE (neuron specific enolase) (categorical split TBD, continuous log base 2)
19. Synaptophysin (categorical split TBD, continuous log base 2)

Three baseline binary AR predictors: 1) AR-V7 status; 2) a composite status (yes/no) of either AR-V7 positive or AR/V-12 positive; and 3) CTC status will be assessed individually, as independent variables, to predict rPFS, time to PSA progression, OS, and composite progression free survival (cPFS) using a single variable Cox model.

Multivariable AR Cox models will then be run on the same endpoints:

- 1) Using log base 2 transformed baseline AR-FL as a covariate in combination with baseline AR-V7 status;
- 2) Using log base 2 transformed baseline AR-FL as a covariate in combination with baseline composite AR-V7/V12 response;

Four baseline continuous log base 2 transformed inflammatory cytokine predictors: 1) IL6, 2) IL8, 3) TNF- α , and 4) sTNF R1 will be assessed individually, as independent variables, to predict rPFS, time to PSA progression, OS, and composite progression free survival (cPFS) using a single variable Cox model.

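### SAP 7.4.3 item 6 divides log2 AR-V7 by log2 AR-FL, which is neither the AR-V7/AR-FL ratio nor its logarithm

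*SAP*

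**What the plan says.** SAP section 6.1.3 (Exploratory Efficacy Endpoints) names the biomarker simply as "AR-V7/AR-FL ratio" and gives no formula.

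SAP section 7.4.3 (Analysis of Exploratory Endpoints) opens with a general rule: "Unless otherwise noted, all continuous biomarker values will be summarized after log base 2 transformation". It then lists 19 items to be described at baseline and at each scheduled visit afterwards. Item 1 includes log2 AR-V7 in positive samples, item 5 is log2 AR-FL, and item 6 is "Ratio of (log base 2 AR-V7)/(log base 2 AR-FL) (for positive status AR-V7").

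On the assay, Protocol section 5.7.1 describes "quantification of messenger RNA (mRNA) of AR-FL, AR variants and GR-FL" by RT-PCR. It states no reporting unit.

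**The concern.** The brackets in item 6 place the logarithm inside both the numerator and the denominator. A programmer following the SAP would log each transcript and then divide. Applying the section's log2 rule to the ratio named in 6.1.3 would give log2(AR-V7/AR-FL), which is a difference of logs and not a quotient.

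The two behave differently. The difference of logs depends only on the relative abundance of the transcripts. The quotient also depends on their absolute level and on the unit. The Protocol synopsis sets out to explore how resistance biomarkers change over time, so a summary that moves when relative AR-V7 expression has not moved would mislead on the question it is meant to describe. A table row labelled as a ratio and showing 0.50 would also be read as AR-V7 at half the AR-FL level, when the true figure could be under 2%.

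**Working it through.** The documents give no numerical value for this endpoint, so there is no plan figure to reproduce. Write a for AR-V7 and b for AR-FL.

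**Algebra**

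- Ratio named in 6.1.3: a/b.
- Its log2: log2(a/b) = log2(a) − log2(b).
- Item 6 as written: log2(a)/log2(b), which is the logarithm of a to base b.

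**Direct evaluation.** All pairs are hypothetical, chosen to show the behaviour.

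| (a, b) | log2 a | log2 b | True ratio a/b | log2 ratio | Item 6 |
|---|---|---|---|---|---|
| (100, 1000) | 6.64 | 9.97 | 0.10 | −3.32 | 0.67 |
| (10, 100) | 3.32 | 6.64 | 0.10 | −3.32 | 0.50 |
| (2, 20) | 1.00 | 4.32 | 0.10 | −3.32 | 0.23 |
| (5, 10) | 2.32 | 3.32 | 0.50 | −1.00 | 0.70 |
| (250, 1000) | 7.97 | 9.97 | 0.25 | −2.00 | 0.80 |
| (2, 4) | 1 | 2 | 0.50 | −1 | 0.50 |
| (4, 16) | 2 | 4 | 0.25 | −2 | 0.50 |
| (8, 64) | 3 | 6 | 0.125 | −3 | 0.50 |
| (64, 4096) | 6 | 12 | 0.016 | −6 | 0.50 |

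- Rows 1 to 3: one true ratio, three different values.
- Rows 4 and 5: the sample with the higher true ratio gets the lower value.
- Rows 6 to 9: one value for true ratios that differ 32-fold (0.50/0.0156).

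**Unit dependence.** Multiply both transcripts by a common factor c. The log2 ratio does not move, because log2(ca) − log2(cb) = log2(a) − log2(b). Item 6 does move:

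| c | (4, 16): item 6 | (64, 1024): item 6 |
|---|---|---|
| 1 | 0.50 | 0.60 |
| 10 | 0.73 | 0.70 |
| 100 | 0.81 | 0.76 |
| 1000 | 0.86 | 0.80 |

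The true ratios are 0.25 and 0.0625 throughout (log2 ratios −2 and −4). The two samples swap order between c = 1 and c = 10, on the unit alone.

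**Edge cases.** At b = 1 the denominator is log2(1) = 0 and the quantity is undefined. Near 1 it is unstable: (2, 1.1) has true ratio 1.8 but gives 1/0.1375 = 7.3. Below 1 the sign can be wrong: (2, 0.5) has true ratio 4 but gives 1/(−1) = −1.

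**How often order would be wrong.** This depends on expression levels and spread, which the documents do not give. Two log-normal simulations with different assumptions give a range.

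- *First set.* AR-FL median 10, 100 or 1000 with log10 SD 0.5 or 0.8; true-ratio median 0.10 with log10 SD 0.4 or 0.6; samples kept if AR-V7 ≥ 1 and AR-FL > 1. The rank correlation of item 6 with the true ratio runs from 0.61 to about 0.95, and 9% to 28% of sample pairs are ordered wrongly. The worst results are at AR-FL median 10, where the filter discards about half the simulated samples. Extending the same spreads to a median of 100,000 lowers mis-ordering to 5% to 12%.
- *Second set.* AR-FL median 10 to 10,000; true-ratio median 0.05 or 0.2; SD of log2 AR-FL 1 or 2; SD of log2 ratio 1.5. Between 4% and 33% of pairs are ordered wrongly.

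**Where item 6 is used.** It appears only in the descriptive list of 7.4.3. The single-variable Cox models for AR use AR-V7 status, the AR-V7/V12 composite and CTC status. The multivariable Cox models add log2 AR-FL as its own covariate. The Fisher tests use AR-V7 status and the composite. The subgroups in SAP 7.8 use CTC detection and AR-V7 status. None of these takes the quotient as input.

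**The case against.** The strongest reply is that this is very small. Item 6 is one exploratory descriptive row in AR-V7-positive samples only. Protocol section 1.2 cites roughly 30–40% positivity after enzalutamide or abiraterone. If that applied here, 0.30 × 40 = 12 to 0.40 × 40 = 16 patients would contribute at baseline. No efficacy or safety conclusion can turn on it. That is accepted, and it sets the limit on the consequence.

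The general log2 rule also allows noted exceptions, and item 6 can be read as one. So the SAP does not strictly break its own rule. But an exception to a transformation rule does not turn a quotient of logs into the ratio named in 6.1.3, and neither document defines or justifies the quotient as a quantity of interest.

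Item 6 may be loose shorthand for the log2 ratio, and the table or data specifications, which are not available here, may program it correctly. That is possible, but the SAP's formula would still need correcting to match. The assay unit may likewise be fixed in the vendor instructions. That would settle which value the quotient takes, but would not make it a ratio.

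The simulated percentages depend on an unknown scale. They show sensitivity and do not forecast this trial's error rate. Finally, a joint fall in both transcripts could be partly seen from items 1 and 5, though item 5 is not restricted to AR-V7-positive samples and so does not match item 6.

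**Conclusion.** The point holds. As written, item 6 is neither the ratio named in SAP 6.1.3 nor its logarithm. It can reverse the order of samples, depends on a unit that the two documents do not state, and is undefined at AR-FL = 1. These are algebraic facts and rest on no assumption about the data. How often samples would be mis-ordered is not known: 4% to 33% of pairs across the assumed scenarios, lowest when expression values are large.

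The effect is limited to one exploratory summary shown by visit. No primary, secondary, Cox, Fisher or subgroup result changes. It should be corrected because the error is certain and the correction costs almost nothing.

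**What to change.** Replace item 6 of SAP 7.4.3 with: log2(AR-V7/AR-FL) = log2(AR-V7) − log2(AR-FL), in AR-V7-positive samples, summarised on the log2 scale and back-transformed to the ratio. Give the same definition beside the entry in SAP 6.1.3.

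As a minor addition, state the reporting unit of the two transcripts and confirm that it is the same for both. A common unit cancels in the difference of logs.

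The cost is one SAP line and one line of code. Both inputs are already summarised in items 1 and 5, so no new data are needed, and SAP section 1 allows revisions before database hard lock.

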All endpoints will be descriptively summarized and their correlation with biomarkers and efficacy endpoints explored via regression models as appropriate. One interim efficacy analysis is planned 13 weeks after the 40th subject is enrolled. Final analysis will be conducted 12 months after last subject is enrolled.

Sample Size Justification:

Prior clinical trials data in the post-chemo setting have shown the following median rPFS for subject randomized to initial placebo, placebo+prednisone, or mitoxantrone+prednisone therapy:

- AFFIRM: Placebo = 2.9 months
- COU-301: Placebo + Prednisone = 3.6 months
- TROPIC: Mitoxantrone + Prednisone = 1.4 months

With a sample size of 40 subjects and an assumed median rPFS of 4 months for the therapy defined in this single-arm study, approximately 34 events are expected over a 12-month accrual and 12-month minimum follow-up. Further assuming uniform accrual, 10% loss to follow-up, and an exponential distribution for the rPFS event times the expected lower bound of the 90% confidence interval for the median is approximately 2.5 months based upon simulations.

Safety:

The severity of all adverse events will be evaluated by the investigator based on the National Cancer Institute's Common Terminology Criteria for Adverse Events (NCI-CTCAE), version 4.0 and all adverse events will be coded to preferred term, higher level term, and system organ class using the Medical Dictionary for Regulatory Activities (MedDRA). The number and percentage of subjects with adverse events will be presented by MedDRA system organ class and preferred term, relationship to study treatment, and maximum CTCAE grade. Descriptive statistics will be used rather than inferential statistics.

Laboratory values will be classified by toxicity grade based on the NCI¬CTCAE, version 4.0. Tables of laboratory CTCAE grade shift from baseline to maximum CTCAE grade across subsequent visits will be provided.

Correlative Studies:

Objectives:

- Explore the prevalence and dynamics of resistance biomarkers
- Explore potential correlation of the resistance biomarkers with rPFS, PSA response, and PSA progression

- Explore potential correlation of the sensitivity biomarkers with rPFS, PSA response, and PSA progression
- Explore potential correlation of inflammatory proteins with rPFS, PSA response, and PSA progression
- Explore potential correlation of AR and glucocorticoid receptor levels and mutations/polymorphism with rPFS, PSA response, and PSA progression

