
Blood samples will be collected to capture CTCs at Week 1, Week 13, and at the time of PSA progression and/or at the time of radiographic progression, for (but not limited to) assessment of the following:

- Expression levels of androgen receptor variants (AR-V's): AR-V7 and AR-V12/ARv567es
- Expression levels of AR full length (AR-FL) and glucocorticoid receptor full length (GR-FL)
- AR mutations e.g. L702H, W741C, F876L and T877A.

Serum samples will be collected at Week 1, Week 13, and at the time of PSA progression and/or at the time of radiographic progression for (but not limited to) inflammatory biomarkers, such as IL6, IL8, Tumor necrotic factor alpha (TNF- α), and soluble TNF receptor-1 (sTNF1), and neuroendocrine (NE) markers such as chromogranin A (CgA), neuron specific enolase (NSE), and synaptophysin.

Sponsor: APGD, Medical Affairs, Americas

ISN/Protocol 9785-MA-1008

- CONFIDENTIAL -

V. SCHEDULE OF ASSESSMENTS

Table 1 Study Schedule of Activities

Study Day	Screening	1	29	57	85	113	141	169	Safety F/U	Unscheduled Visit ^a	Long-
	Visit									Visit	term
*** 1	4.4	_	-	_	12	4.7	2.1	25 1	20.1 6	,	F/U
Week	-4 to -1	1	5	9	13	17	21	25 and every	30 days after	n/a	Every 12
	(28 days)							subsequent 12 weeks	last dose ^b		weeks
Window (days)			± 3	±3	± 3	± 3	± 3	± 3	± 7	n/a	± 7
Informed Consent	X										
Medical History	X										
Inclusion/Exclusion Criteria	X	X									
Vital Signs	X	X	X	X	X	X	X	X	X	X	
Physical Examination ^c , Weight ^d	X ^d	X	X	X	X	X	X	X	X	X	
12-Lead ECG	X										
MUGA/Echocardiogram ^e	X										
Clinical Labs ^f	X	X^{g}			X			X	X	X	
PSA ^h	X	X		X	X	X	X	X	X		
CT/MRI and Bone Scan ¹	X			X		X		X			
CXR or Chest CT	X										
ECOG PS	X	X			X			X	X	X	
Adverse Events ¹	X	X	X	X	X	X	X	X	X	X	
Concomitant Medications	X	X	X	X	X	X	X	X	X	X	
Study Drug Dispensing		X	X	X	X	X	X	X			
Long-Term F/U Assessments ^k											X
Study Drug Treatment ¹		X	X	X	X	X	X	X			
Blood Samples for CTCs and molecular		X			X						
profiling ^m											
Serum Samples ^m		X			X						

^a Unscheduled visits may be performed at any time during the study whenever necessary to assess for or follow up on adverse events, at the patient's request or if deemed necessary by the investigator.

Footnotes continued on next page

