To date, a study of enzalutamide re-treatment following enzalutamide and intervening chemotherapy has not been performed. Limited data are available on re-treatment with an AR-targeting agent. A retrospective review of a small cohort of patients that received AA re-treatment (n=12), no biochemical response was observed among patients who did not initially respond to AA; among the 7 patients who initially responded to AA, upon re-treatment, the rate of PSA reduction by 30% and 50% was 86% and 46%, respectively. Given the similarity in MOA, evaluation of enzalutamide re-treatment in men with limited other therapeutic options is warranted [Leibowitz-Amit et al, 2014].

Rationale for chemotherapy prior to Enzalutamide re-treatment

Docetaxel may overcome resistance to enzalutamide in a manner that is both AR-dependent and AR-independent. Recent work suggests that the microtubule network of prostate cells is critical for androgen receptor nuclear translocation and activity. Unlike AR-V7, ARv567es/AR-V12 has hinge domain. This allows ARv567es/AR-V12 to co-sediment with microtubules or co-precipitate with dynein motor protein in the same way as AR-FL. Docetaxel was shown to suppress ARv567es/AR-V12 nuclear translocation and transcription activation [Thadani-Mulero et al, 2014]. In addition, being a cytotoxic agent, docetaxel has been shown to induce mitotic catastrophe subsequent to G2/M arrest, and activation of bcl-2 and bcl-xL gene dependent and independent apoptotic pathways [Fabbri et al, 2008]. This provides the AR-independent mechanism of overcoming the resistance. The study will enroll patients who have received at least 4 cycles of docetaxel and/or cabazitaxel to allow a

selection of a subset of patients for whom chemotherapy can overcome resistance. AR-V7 and AR-V12, as well as AR mutations will be studied to help assess response to enzalutamide re-treatment.

Cabazitaxel may overcome resistance to enzalutamide in a similar manner as docetaxel. Cases of reversions from AR-V7 positive to negative status following cabazitaxel treatment have been reported [Nakazawa et al, 2015].

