7.4.3 Analysis of Exploratory Endpoints

Descriptive statistics (e.g., N, mean, standard deviation, minimum, median, maximum, frequency, and percentage) will be provided for baseline blood and plasma samples and by each post-baseline scheduled timepoint.

Baseline biomarker measurements will be included in regression models to assess correlation with the following endpoints: rPFS, time to OS, PSA30, PSA50, PSA90, and objective response. Time-to-event data endpoints will be modelled via Cox proportional hazards model. Binary endpoints will be modeled via logistic regression. Univariate models will be used to assess significance of individual biomarker measures. Multivariable models may also be considered to control for baseline demographic, disease, and treatment characteristics.

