Three baseline continuous log base 2 transformed neuroendocrine predictors: 1) CgA, 2) NSE, and 3) synaptophysin will be assessed individually, as independent variables, to predict rPFS, time to PSA progression, OS, and composite progression free survival (cPFS) using a single variable Cox model.

Hazard ratio point estimates, n, standard errors, p-values, and 90% confidence intervals will be displayed in a single table for all the AR, inflammatory cytokine, and neuroendocrine Cox models.

KM plots, medians, and 90% confidence intervals for the binary AR predictors will be presented for rPFS, time to PSA progression, OS and cPFS.

Waterfall plot of maximum reduction in PSA from baseline with AR-v7, AR-v12, and AR mutation status labeled on the plot.

The AR-V7 and the composite AR-V7/V12 composite predictors will be individually assessed as an independent variables to predict PSA30, PSA50, PSA90, and objective response using Fisher's exact test. Note that objective response will be evaluated using subjects that are both BAS and have measureable disease.

Counts, frequencies, differences in frequencies and 90% Clopper-Pearson methodology will be displayed for the binary AR predictors.

Reported p-values for hazard ratios will use Wald (chi-square) test statistics, and p-values for comparing Kaplan-Meier curves will use log-rank (score) test statistics. Breslow method will be used for handling ties.

In the event that additional exploratory analyses are required for the Clinical Study Report, the SAP will be amended accordingly.

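### SAP 7.4.3 drops, without a stated reason, biomarker models that the protocol commits to: none for GR-FL, and none relating cytokines, neuroendocrine markers, AR-FL or GR-FL to PSA response

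*SAP*

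**What the plan says.** Protocol Synopsis, Correlative Studies, sets these objectives among others:

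- For the two receptors, the stated aim is this: "Explore potential correlation of AR and glucocorticoid receptor levels and mutations/polymorphism with rPFS, PSA response, and PSA progression"
- The cytokines have their own line, worded in parallel: "Explore potential correlation of inflammatory proteins with rPFS, PSA response, and PSA progression"
- A broader line covers resistance and does not itemise the markers meant: "Explore potential correlation of the resistance biomarkers with rPFS, PSA response, and PSA progression"

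The same section lists among the measures to be taken "Expression levels of androgen receptor variants (AR-V's): AR-V7 and AR-V12/ARv567es".

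Protocol 7.4.3 gives the method. Baseline biomarkers go into regression models for rPFS, OS, PSA30, PSA50, PSA90 and objective response, with Cox for times and logistic for binary endpoints. It adds: "Univariate models will be used to assess significance of individual biomarker measures". Only the multivariable models are optional.

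SAP 7.4.3 then lists its models:

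- Single-variable Cox models of rPFS, time to PSA progression, OS and cPFS on "Three baseline binary AR predictors: 1) AR-V7 status; 2) a composite status (yes/no) of either AR-V7 positive or AR/V-12 positive; and 3) CTC status", on four cytokines, and on three neuroendocrine markers.
- Two Cox models that add log2 AR-FL as a covariate, one to AR-V7 status and one to the composite.
- For binary outcomes, Fisher's exact tests only: "The AR-V7 and the composite AR-V7/V12 composite predictors will be individually assessed as an independent variables to predict PSA30, PSA50, PSA90, and objective response".
- A waterfall plot of PSA reduction labelled with AR-V7, AR-V12 and mutation status.

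GR-FL appears only in the list of descriptive summaries. The four AR mutations are marked there as descriptive only.

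**The concern.** The SAP is meant to carry out the protocol's analyses in more detail. Here it replaces a general commitment, one univariate model per biomarker, with a shorter closed list. Some markers that the objectives name fall off that list.

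Run exactly as written, the study would measure GR-FL and report no association with any outcome. It would measure four cytokines and three neuroendocrine markers and report no association with PSA response. Both documents place correlative science among the secondary objectives, although the endpoint itself is exploratory.

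The remaining route is a later SAP amendment. In an open-label study that means choosing markers when outcomes may already be known. The SAP's own Introduction links early finalisation in an open-label study to avoiding bias.

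**Working it through.** **Context: the plan's sizing figure.** Inputs from SAP section 4: N = 40, median rPFS 4 months, exponential times, uniform 12-month accrual, 12 to 24 months of follow-up, 10% loss.

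- λ = ln 2 / 4 = 0.1733 per month.
- P(event) = 1 − (e^(−12λ) − e^(−24λ)) / (12λ) = 1 − (0.1250 − 0.0156) / 2.079 = 0.947.
- Events = 40 × 0.9 × 0.947 = 34.1, against about 34 stated.

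The figure reproduces when the lost 10% are counted as contributing no events. The point below does not rest on it. It shows only how little information any biomarker model will have.

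**The check: markers against models.** SAP 7.4.3 lists 19 summary items. Leaving out the AR-V7 change-from-baseline item (not a baseline marker) and the AR-V7/AR-FL ratio (a derived quantity, also unmodelled) gives 17 baseline markers.

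| Baseline marker | Single-variable Cox | Test against PSA30/50/90 and objective response |
|---|---|---|
| AR-V7 | yes | Fisher |
| AR-V7/V12 composite | yes | Fisher |
| CTC status | yes | no Fisher test (PSA30 by subgroup, SAP 7.8) |
| IL6, IL8, TNF-α, sTNFR1 | 4 of 4 | 0 of 4 |
| CgA, NSE, synaptophysin | 3 of 3 | 0 of 3 |
| AR-FL | no, covariate only | none |
| GR-FL | none | none |
| AR-V12 alone | none | none (waterfall label) |
| L702H, W741C, F876L, T877A | 0 of 4 | 0 of 4 (waterfall label) |

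Totals: Cox 1 + 1 + 1 + 4 + 3 = 10 of 17; Fisher tests 2 of 17.

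**Does another section fill the gap?** SAP 7.8 adds subgroups by CTC detection and AR-V7 only. SAP 7.4.4 and 7.9 are marked not applicable. No logistic model appears anywhere in the SAP. SAP 6.1.3 does not list AR-V12 at all, although 7.4.3 uses it.

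**Objective by objective.**

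- GR level: 0 of 3 named outcomes analysed.
- Inflammatory proteins: 2 of 3 (rPFS and PSA progression are modelled, PSA response is not).
- AR level through AR-FL: adjusted estimates only for rPFS and PSA progression, nothing for PSA response.
- AR mutations: descriptive only.
- Neuroendocrine markers: the Synopsis objectives do not name them. The commitment comes from Protocol 7.4.3, which covers baseline biomarkers generally.

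**Size of the planned set.** Single-variable Cox 10 × 4 = 40; AR-FL covariate models 2 × 4 = 8; Fisher 2 × 4 = 8. Total 56.

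**The case against.** The best defence is that this is exploratory work in 40 subjects. The Synopsis says correlations are explored through regression as appropriate, SAP 7.4.3 allows amendment for further exploratory analyses, and a shorter list limits chance findings. Fisher's exact test is also safer than ordinary logistic regression when few subjects reach PSA90, because logistic estimates can fail through separation.

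Part of this stands. The endpoints are exploratory, separation is a real risk that any added logistic model must handle, and more estimates mean more noise. But small numbers apply equally to the 10 markers that keep Cox models, so they do not explain why GR-FL is left out. Fisher's test also cannot serve continuous markers without a cut-point.

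A reader might go further on AR-V12. Protocol 1.2 contrasts it with AR-V7 and says "Docetaxel was shown to suppress ARv567es/AR-V12 nuclear translocation and transcription activation". One might infer that the composite pools opposite effects and could hide them, or that a model of AR-V12 alone would test whether taxane reverses AR-V12-driven resistance. The documents support neither inference:

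- Protocol 1.2 also groups AR-V7 and ARv567es as constitutively active variants when it discusses enzalutamide resistance, which favours an either-positive composite.
- Nothing in either document suggests that AR-V12 positivity is protective on enzalutamide.
- The docetaxel statement concerns the taxane. This is a single-arm study in which eligibility requires prior taxane and no sample precedes it, so no added baseline model could estimate reversal.
- AR-V12 status is already shown against PSA decline on the waterfall plot, though without an estimate.

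**Conclusion.** This is an unexplained conflict between the protocol and the SAP, established by reading the two side by side and not dependent on any assumed effect size. GR-FL has no association analysis. AR-FL has no model of its own. AR-V12 alone has summaries and a plot label but no estimate. Nine continuous markers (GR-FL, AR-FL, four cytokines, three neuroendocrine markers) are not related to PSA30, PSA50 or PSA90, which leaves 9 × 3 = 27 marker-by-endpoint combinations empty, or 9 × 4 = 36 with objective response.

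It would be too strong to say that the correlative objectives cannot be answered. The samples are collected, the cytokine objective is met for two of its three outcomes, and the SAP can be amended. The gap is in what the SAP would produce as written. It is worth correcting because correction is cheap, but it affects no primary or secondary efficacy endpoint result.

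**What to change.** In SAP 7.4.3:

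1. Add single-variable Cox models of rPFS, time to PSA progression, OS and cPFS on log2 GR-FL and on log2 AR-FL (2 × 4 = 8 estimates).
2. Add single-variable logistic models of PSA30, PSA50, PSA90 and objective response on log2 GR-FL, AR-FL, IL6, IL8, TNF-α, sTNFR1, CgA, NSE and synaptophysin (9 × 4 = 36 estimates). Specify exact or Firth-penalised logistic regression where responders are few.
3. Show AR-V12 status beside the composite with its 90% CI, descriptively. Add AR-V12 to the marker list in SAP 6.1.3.
4. Put the binary-endpoint results in a separate odds-ratio table, since the planned table holds hazard ratios, and label all additions exploratory.
5. State that the AR mutations, which the same objective names, are analysed descriptively only.

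If the sponsor prefers to leave any of these out, the SAP should record which and why.

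Cost: 8 + 36 = 44 model estimates plus a few AR-V12 rows, so roughly 40 to 50 on top of the 56 planned. Some will be imprecise and should be read through their intervals. No new samples or visits are needed, and the sample size is unchanged.
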